Investigational Device	
Web Information Tool (WIT) - A web-based software providing additional information regarding glucose variability, estimated A1c, risks for hypo- and hyperglycemia, and potential changes of insulin pump parameters, to users of the Control-IQ system. The WIT is the clinical implementation of the ABC concept, which includes the following modules:
 
• Behavioral Anticipation Module (BAM) - an app running on a smart phone which provides on-demand information to the participant primarily on glycemic risks.• Auto Titration Module (ATM) that provides recommendations to the participant to periodically update insulin parameters.• Web Simulation Tool (WST) - is intended to allow users of the Control-IQ system replay treatment scenarios in computer simulation, thereby allowing user training with carbohydrate and insulin action.
Investigational Medication	None
Objectives	Assess the safety and feasibility of two modules (BAM and ATM / WST) used in conjunction with an FDA approved automated insulin delivery system (t:slim X2 with Control-IQ technology)
Study Design	Randomized parallel group trial.
Number of Sites	1
Endpoint	
Primary Outcome: Safety assessment of ATM / WST and BAM modules.
 
Secondary Outcomes:
 
• Percent of readings in the target ranges of 70-180 and 70-140 mg/dL• Other CGM-based metrics;• Questionnaires addressing BAM and participant preferences for system/technology use.
Population	
Key Inclusion Criteria
 
• Age 18-70, inclusive, with Type 1 Diabetes for at least one year• Current user of t:slim X2 insulin pump with Control-IQ Technology 
Key Exclusion Criteria
 
• Recent severe hypoglycemic event or DKA during the past one year
Sample Size	Recruit up to 45 participants of Control-IQ with the objective of randomizing 30 subjects
Treatment Groups	
• Group 1: Control-IQ + Auto Titration Module (ATM) and Web Simulation Tool (WST) for 6 weeks• Group 2: Control-IQ + Auto Titration Module (ATM) and Web Simulation Tool (WST) +Behavioral Adaptation Module (BAM) for 6 weeks
Participant Duration	8 weeks

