373 repeated. These may be repeated at the discretion of the Principal Investigator

374 Individuals who do not initially meet study eligibility requirements may be rescreened at a later
375 date per investigator discretion.

CLINICAL PROTOCOL

376 **4.4 Participant Inclusion Criteria**

377 The participants must meet all the following inclusion criteria in order to be eligible to participate
378 in the study.

- 379 1. Age ≥ 18.0 and ≤ 70 years old at time of consent
- 380 2. Clinical diagnosis, based on investigator assessment, of type 1 diabetes for at least one
381 year
- 382 3. Currently using insulin pump for at least six months
- 383 4. Currently using insulin for at least six months
- 384 5. Currently using or anticipated to be using the t:slim X2 insulin pump with Control-IQ
385 technology at the start of the run-in phase (Visit 1).
- 386 6. Using or willing to use insulin parameters such as carbohydrate ratio and correction
387 factors consistently on their pump in order to dose insulin for meals or corrections
- 388 7. Access to internet and willingness to upload data during the study as needed
- 389 8. Willing to use an app on a smart phone during the study.
- 390 9. For females, not currently known to be pregnant or breastfeeding
- 391 10. If female, sexually active, and of childbearing potential, must agree to use a form of
392 contraception to prevent pregnancy while a participant in the study. A negative serum or
393 urine pregnancy test will be required for all females of childbearing potential. Participants
394 who become pregnant will be discontinued from the study. Also, participants who during
395 the study develop and express the intention to become pregnant within the timespan of
396 the study will be discontinued.
- 397 11. Willingness to use only insulin analogs approved for use in the t:slim X2 pump such as
398 lispro (Humalog) or aspart (Novolog) and not use ultra-rapid acting insulin analogs (e.g.
399 FiAsp) during the study
- 400 12. Total daily insulin dose (TDD) at least 10 units per day
- 401 13. Willingness not to start any new non-insulin glucose-lowering agent during the course of
402 the trial (including metformin, GLP-1 agonists, pramlintide, DPP-4 inhibitors, biguanides,
403 and sulfonylureas)
- 404 14. An understanding and willingness to follow the protocol and signed informed consent

405 **4.5 Participant Exclusion Criteria**

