472 If an exclusionary condition is identified, the study participant will be excluded from participation
473 with follow up and referral to their primary care physician as needed.

474 If the study participant is pregnant, the study physician will discuss the results of the blood test
475 with the participant and the participant will be asked to seek confirmation of the test and the
476 appropriate medical care.

CLINICAL PROTOCOL

- 477 Participants may be re-screened at a later date if their clinical situation changes as determined
- 478 by the study physician.

CLINICAL PROTOCOL

479 **Chapter 5: Study Equipment Training**

480 Equipment training relevant to the study visit may begin immediately after screening eligibility
481 has been met or may be deferred for a maximum of 30 days.

482 All participants will be asked to use their personal t:slim X2 insulin pump with Control-IQ
483 Technology and study Dexcom G6 CGM throughout the study period from Run-In Visit through
484 the Final Study Visit. Study supplied phones will be available upon request.

485 Study contact information will be provided to the participant. The study team will be available by
486 phone as needed throughout the study duration.

487 All study training may be performed as an office visit, or via telecommunication.

488 **5.1 CGM Training**

489 A Dexcom G6 CGM will be provided to all participants at the training session. The participants
490 may choose to use their personal CGM equipment or will be provided with study CGM
491 equipment. Participants will be instructed to use the study CGM on a daily basis. If the participant
492 has prior use of the CGM, re-training will be specific to the individual. The study team may elect
493 to have less frequent CGM users watch the Dexcom online training videos
494 (<https://www.dexcom.com/training-videos>) to assist in the training session.

495 The participants will be asked to perform fingerstick blood glucose measurements (if needed) in
496 accordance with the labeling of the CGM device.

497 **5.2 Insulin Pump Training**

498 Participants are current users of Control-IQ and therefore do not require training on the pump.
499 The participant will be instructed on how to use the system if insulin is delivered by any means
500 other than the Control-IQ pump (e.g. injection of subcutaneous insulin via syringe in the event of
501 infusion site failure). If insulin is delivered by any means other than the study pump, the

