598 are completed and eligibility determined. This visit may occur as an in-person office visit or via
599 telecommunication. For visits occurring remotely, these relevant devices will be shipped to the
600 participant.

601 The purpose of the run-in phase is to obtain about 14 days of baseline data while the participant
602 is following their usual care with their personal t:slim X2 study pump and Dexcom G6 CGM. The
603 study team may elect to allow the participant to repeat the run-in phase as needed.

604 At Visit 2, participants will be trained on the CGM and insulin pump, if relevant, as described in
605 section 5.1 and 4.2. Participants will also be trained on blood glucose meter if relevant and the
606 ketone meter as described in section 5.5 and 4.6.

607 A pregnancy test will be repeated as needed if more than 30 days has elapsed since the
608 prior pregnancy test.

609 Study clinicians may optimize insulin pump settings if needed during this visit. Participants will
610 be allowed to make insulin dosing decisions per their usual care but will be asked to avoid
611 changing insulin pump settings during the two-week run-in.

612 **6.2 Randomization Visit (Visit 3)**

613 **6.2.1 Randomization Criteria**

614 After the completion of at least 2 weeks of run-in data, participants will have a randomization
615 visit. This visit can occur between 14-28 days from Visit 2. This visit can be conducted either in-
616 person office visit or as a remote visit.

617 Screening failures and study dropout participants may be replaced.

618 This visit may be performed as an office visit, or via telecommunication.

619 **6.2.2 Participants**

620 Participants will be randomized 1:1 to either:

621 • Group 1: Use of AID and ATM / WST for 6 weeks

CLINICAL PROTOCOL

622 • Group 2: Use of AID, ATM / WST, and BAM for 6 weeks

623 The randomization scheme will be completed prior to the first study participant and will be done
624 by a study team member who is not involved with enrollment.

625 **6.3 Optimization of Insulin Pump Settings**

626 Insulin pump optimization will occur during the study as described in Section 4.2.1.

627 **6.4 Check-In Visits (Visit 4-8)**

628 These visits will occur either as in-person office visits or remote visits. These visits will occur
629 weekly (+/- 3 day). Prior to each phone visit, participants will be asked to download any relevant

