1013 collaborators involved in the study after the appropriate research agreement has been executed.

CLINICAL PROTOCOL

1014 Chapter 11: Statistical Consideration

1015 The intent of this pilot-feasibility study is to introduce and initially test elements of two modules
1016 to be included in a future Adaptive Biobehavioral Control (ABC) system: (1) A Behavioral
1017 Adaptation Module (BAM) and (2) An Auto Titration Module (ATM) and a Web Simulation Model
1018 (WST). BAM and ATM / WST will be provided to users of the t:slim X2 with Control-IQ closed-loop
1019 system. The only purpose of this trial is safety testing and receiving feedback from the
1020 participants regarding system functionality and user interface.

1021 11.1 Design and Randomization

1022 The study will recruit current users of the Control-IQ system. Following a 2-week baseline using
1023 Control-IQ only, the participants will be randomized 1:1 to Control-IQ + ATM / WST vs Control IQ
1024 + ATM / WST + BAM and will be followed for 6 weeks. The randomization list will use a sequence
1025 of computer-generated pseudorandom Bernoulli trials. The 6 weeks of active trial will be used
1026 for assessment of the safety and usability of ATM / WST and BAM. The baseline data and the last
1027 2 weeks of the active trial will be used for secondary comparisons of CGM-based metrics of
1028 glycemic control.

1030 11.2 Sample Size

1031 We intend to recruit up to 45 users of Control-IQ, with the objective to randomize N=30 subjects.
1032 The number of participants is a convenience sample not based on statistical principles. This
1033 sample will provide ~180 weeks of data for the assessment of the safety and utility of the ATM
1034 and up to 90 weeks for assessment of the safety and utility of the BAM.

1035 11.3 Outcome Measures

1036 11.3.1 Primary Efficacy Endpoint

1037 Safety assessment of ATM / WST and BAM.

1038 11.3.2 Secondary Outcome

1039 CGM-based metrics and user experience (UX) questionnaires, including:

CLINICAL PROTOCOL

1040 • Percentage of readings in the target ranges of 70-180 and 70-140 mg/dl;
1041 • Mean glucose;
1042 • Glucose variability measured by standard deviation and coefficient of variation;
1043 • Percentage of readings <70, 60, and 54 mg/dl;
1044 • Low blood glucose index (LBGI)¹⁰
1045 • Percentage of readings >180, 250, and 300 mg/dl;
1046 • High blood glucose index (HBGI)¹⁰
1047 • ABC Pilot Pre and Post Study Questionnaire
1048 • INSPIRE

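### Inclusion criterion 5 admits people not yet on Control-IQ, against the current-user population described elsewhere, so some baselines could fall in early closed-loop use and could bias the two secondary comparisons with baseline

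*Combined protocol and SAP*

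**What the plan says.** The criterion that sites will apply is section 4.4, item 5. It takes a person "Currently using or anticipated to be using the t:slim X2 insulin pump with Control-IQ" "technology at the start of the run-in phase (Visit 1"). Three other places describe a narrower population:

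- Synopsis, key inclusion criteria: "Current user of t:slim X2 insulin pump with Control-IQ Technology".
- Section 5.2: "Participants are current users of Control-IQ and therefore do not require training on the pump".
- Section 11.1: "The study will recruit current users of the Control-IQ system".

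The nearest duration rule is item 3 of 4.4, "Currently using insulin pump for at least six months". It concerns any pump, not Control-IQ. Item 4 asks for six months on insulin. No section sets a minimum time on Control-IQ.

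Table 1 and section 6.1 place the run-in at Visit 2. Section 6.1 lets that visit take place on the day of screening or up to 30 days after screening is complete. It describes the baseline as follows: "The purpose of the run-in phase is to obtain about 14 days of baseline data while the participant" follows usual care on a personal pump and CGM. Section 2.7 then plans three secondary comparisons of CGM metrics: each group's last two treatment weeks against its own baseline, and Group 1 against Group 2.

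**The concern.** A baseline is useful for a before-after comparison only if the person is in a steady state on the background treatment. A person who begins Control-IQ at or just before Visit 2 may still be settling in during the run-in. Any further improvement by weeks 5 and 6 would then be counted as an effect of the modules in that group's comparison with baseline.

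The protocol's own rationale makes this plausible. Sections 1.1 and 2.1 say that the person must adapt to closed-loop control, and BAM exists to help with that adaptation. Unaided settling-in would look like the effect being sought. The model in 11.7 adjusts for age and HbA1c but not for time on Control-IQ, so it would not separate the two.

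**Working it through.** **1. The texts side by side.** Item 5 allows present or expected use. The synopsis and 11.1 allow present use only, and 5.2 relies on present use to waive pump training. Section 6.1, however, leaves room for such training: "At Visit 2, participants will be trained on the CGM and insulin pump, if relevant, as described in" sections 5.1 and 4.2. The time of the check is also unclear. If item 5's Visit 1 is taken literally, Control-IQ must be in use by screening; if the start of run-in is meant, use by Visit 2 is enough. Because both visits may fall on one day, neither reading guarantees any Control-IQ use before the baseline starts.

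**2. The plan's own figures.** Section 11.2 bases no sample size on power. Its data volumes reproduce: 30 × 6 = 180 weeks for ATM, and 15 × 6 = 90 weeks for BAM. The second implies about 15 per group.

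**3. Bias in a comparison with baseline.** Let f be the share of new starters in a group and d their mean change in time in range (TIR, percentage points) from run-in to weeks 5 and 6 that is due to settling in alone. Then bias = f × d. The documents give neither input, so the values below are assumptions.

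| New starters among 15 | d = 5 | d = 10 |
|---|---|---|
| 0 | 0 | 0 |
| 1 | 1/15 × 5 = 0.33 | 0.67 |
| 3 | 3/15 × 5 = 1.0 | 2.0 |
| 5 | 5/15 × 5 = 1.67 | 3.33 |

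If d = 0, the bias is zero whatever the share.

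**4. Bias against sampling error.** Take the ±11 in the TIR success criterion of 11.4 as a between-person SD (an assumption), and let ρ be the assumed correlation between baseline and follow-up. The standard error of a group's mean change is 11 × √(2(1 − ρ)) / √15, which is 2.84, 2.20 and 1.80 points for ρ = 0.5, 0.7 and 0.8. The error rate of a two-sided test (5% assumed, since 11.7 gives no level) under a normal approximation shifted by bias/SE is:

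- 1 new starter, d = 5: 5.2% to 5.4%.
- 3 new starters, d = 5: 6.4% to 8.6%.
- 5 new starters, d = 10: 22% to 46%.

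**5. Group 1 against Group 2.** Randomization makes the expected difference in the number of new starters zero, so there is no systematic bias. Chance imbalance adds noise. Given a 15:15 split and d = 5, its SD is 0.46, 0.74 or 0.88 points for 2, 6 or 10 new starters among the 30.

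**The case against.** A reader might infer that some baselines will be the first two weeks of closed loop, and that both comparisons with baseline will therefore be biased. The documents do not support that. Item 5 permits new starters but does not show that any will enrol. A person who only expects to use Control-IQ at screening may gain some weeks of use in the gap of up to 30 days. Six months of pump experience is required, the pump is the participant's own, and the team may repeat the run-in. A start on the first day of run-in is the extreme case. These points stand, and they limit the finding to a possibility. None of them rules the case out.

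The conflict with the current-user texts can also be softened. The synopsis lists only key criteria. Section 5.2 could be true at Visit 2 if everyone has started by then, and 6.1 provides for training where relevant. That is fair for the synopsis and 5.2. Section 11.1 describes who will be recruited, and there the conflict is plainest.

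The affected comparisons are secondary and uncontrolled, in a convenience-sample pilot, and are open to time trends even among established users. This limits the importance of the point, but it is no reason to leave in an avoidable source of bias.

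Finally, the relevant d is not the benefit of starting Control-IQ. It is only the further change after a run-in already on Control-IQ. The documents support such a change in words only, without size or duration.

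**Conclusion.** The inconsistency in the text is certain: item 5 is wider than the population described in the synopsis, 5.2 and 11.1, and its visit label disagrees with Table 1 and 6.1. Since no minimum time on Control-IQ is set and the analysis does not adjust for it, the plan as written allows baselines in early closed-loop use. These could bias the ATM / WST and the ATM / WST + BAM comparisons with baseline.

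The size of any bias is unknown. The 1-point example (3 of 15, 5-point gain) and the error rates above depend wholly on assumed inputs and are not evidence that bias will occur. One new starter would hardly matter; several with a large gain would. The randomized comparison is unbiased in expectation. The primary outcome in 2.6, DKA or severe hypoglycemia over the six treatment weeks, does not use the baseline and is unaffected by this bias.

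**What to change.** Reconcile item 5 with the synopsis, 5.2 and 11.1 so that Control-IQ must be in use before the run-in begins, name that point as Visit 2, and state a minimum period of prior use chosen by the sponsor. Deleting the reference to anticipated use would not be enough by itself, because a person who started the day before would still count as a current user.

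If the sponsor keeps the wider wording for recruitment, bring the other three places into line with it, record each participant's Control-IQ start date, and pre-specify a sensitivity analysis of the two comparisons with baseline that leaves out new starters, with that term defined in advance. The main analysis should keep everyone, because 11.7 puts all randomized participants into the secondary CGM analyses. Dropping new starters from the main analysis would create a new contradiction.

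The cost is a short eligibility amendment and a slightly smaller recruitment pool. The alternative costs one recorded date and one extra analysis.

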303 This is a safety and feasibility study with a randomized two-arm parallel group trial in which both
304 groups will use the AID (Control-IQ) plus ATM and WST. The difference between the two groups
305 will be the behavioral module. One group will be randomized to add BAM and one group will not
306 use BAM. This is illustrated in Figure 2:

CLINICAL PROTOCOL

307

308 **Figure 3: Study Diagram**

309 **2.3 Purpose/Objectives of Clinical Study**

310 This pilot study is intended to test a Web-based Information Tool (WIT) software providing
311 additional information regarding glucose variability, estimated A1c, risks for hypo- and
312 hyperglycemia, and potential changes of insulin pump parameters, to users of the Control-IQ
313 system.

314 **2.4 Study Participants**

315 Enrollment in the study will proceed with the goal of completing approximately 30 subjects.
316 Study duration is between 8-10 weeks.

317 Up to 45 participants may sign the consent form.

318 **2.5 Clinical Sites**

319 The study will be performed at the University of Virginia.

320 **2.6 Primary Specific Aim**

321 The primary outcome will be a safety assessment using all 6 weeks of treatment data in terms of
322 incidence of DKA or severe hypoglycemia.

323 **2.7 Secondary Specific Aim**

324 The secondary outcome of interest will be primarily CGM-based metrics using the last two weeks
325 of the treatment data and the two-week baseline to compare:

326 • ATM / WST vs. Baseline
327 • ATM / WST + BAM vs. Baseline
328 • Group 1 vs. Group 2: ATM / WST vs. ATM / WST + BAM.

CLINICAL PROTOCOL

329 **Chapter 3: Study Devices**

330 **3.1 Insulin Pump**

331 Participants will use their personal FDA-approved Tandem t:slim X2 with Control-IQ Technology
332 which will be used without modifications.

333 **3.2 Continuous Glucose Monitor**

334 Participants will be provided a study provided CGM that includes Dexcom G6 transmitter and
335 sensors while using the Tandem t:slim X2 insulin pumps. The CGM sensor is viable for 10 days.
336 All participants will be provided a Dexcom G6 system by the study team as needed. This system
337 will be used without modifications. The CGM device will be calibrated, if needed, using the
338 glucometer in accordance with the manufacturer's labeling. The participant may elect to
339 continue use of their personal CGM during the study. The study will provide CGM supplies, as

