858 neuroglycopenia to induce seizure or coma;

CLINICAL PROTOCOL

859 • if plasma glucose measurements are not available during such an event, neurological
860 recovery attributable to the restoration of plasma glucose to normal is considered
861 sufficient evidence that the event was induced by a low plasma glucose concentration.

862 **9.2.2 Hyperglycemia Events/Diabetes Ketoacidosis**

863 Hyperglycemia not associated with an Adverse Device Effect is only reportable as an adverse
864 event when one of the following four criteria is met:

865 • the event involved DKA, as defined by the Diabetes Control and Complications Trial
866 (DCCT) and described below
867 • evaluation or treatment was obtained at a health care provider facility for an acute event
868 involving hyperglycemia or ketosis
869 • blood ketone level ≥ 1.5 mmol/L and communication occurred with a health care provider
870 at the time of the event
871 • blood ketone level ≥ 3.0 mmol/L, even if there was no communication with a health care
872 provider

873 Hyperglycemic events are classified as DKA if the following are present:

874 • symptoms such as polyuria, polydipsia, nausea, or vomiting;
875 • serum ketones ≥ 1.5 mmol/l or large/moderate urine ketones;
876 • treatment provided in a health care facility
877 • all reportable Adverse Events—whether volunteered by the participant, discovered by
878 study personnel during questioning, or detected through physical examination,
879 laboratory test, or other means—will be reported on an adverse event form online.

880 **9.3 Relationship of Adverse Event to Study Device**

881 The study investigator will assess the relationship of any adverse event to be related or unrelated
882 by determining if there is a reasonable possibility that the adverse event may have been caused
883 by the study device.

884 To ensure consistency of adverse event causality assessments, investigators should apply the
885 following general guideline when determining whether an adverse event is related:

886 • There is a plausible temporal relationship between the onset of the adverse event and
887 the study intervention, and the adverse event cannot be readily explained by the
888 participant's clinical state, intercurrent illness, or concomitant therapies; and/or the
889 adverse event follows a known pattern of response to the study intervention; and/or the

CLINICAL PROTOCOL

890 adverse event abates or resolves upon discontinuation of the study intervention or dose

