9.9.2 Suspending/Stopping Overall Study

In the case of an unanticipated system malfunction resulting in a severe hypoglycemia or severe hyperglycemia event (as defined in section 9.2), use of the study device system will be suspended while the problem is diagnosed.

CLINICAL PROTOCOL

986 In addition, study activities could be similarly suspended if the manufacturer of any constituent
987 study device requires stoppage of device use for safety reasons (e.g. product recall). The affected
988 study activities may resume if the underlying problem can be corrected by a protocol or system
989 modification that will not invalidate the results obtained prior to suspension. Definition of a Data
990 Breach.

991 The study must also stop if there are three severe hypoglycemia events or three DKA events.
992 After further medical/safety review of the events, the study may resume if the events are
993 determined to be unrelated to an unanticipated system malfunction.

994 A data breach is defined in the HITECH Act (43 USC 17932) as an unauthorized acquisition, access,
995 or use of protected health information (PHI) that compromises the security or privacy of such
996 information.

CLINICAL PROTOCOL

997 **Chapter 10: Miscellaneous Considerations**

998 **10.1 Prohibited Medications, Treatments, and Procedures**

999 Participants using non-approved insulins at the time of enrollment will be asked to contact their
1000 personal physician to change their prescribed personal insulin to a rapid-acting insulin approved
1001 for use in the t:slim X2 pump (e.g. lispro or aspart) for the duration of the trial.

1002 The devices (insulin pump, CGM) must be removed before Magnetic Resonance Imaging (MRI),
1003 Computed Tomography (CT) or diathermy treatment. Participants may continue in the trial after
1004 temporarily discontinuing use if requiring one of the treatments above.

1005 **10.2 Participant Withdrawal**

1006 Participation in the study is voluntary. Participant may withdraw at any time. For participants
1007 who do withdraw from the study, the study team will determine if their data will be used in
1008 analysis.

1009 **10.3 Confidentiality**

[figure not shown]
1010 For security and confidentiality purposes, subjects will be assigned an identifier that will be used
1011 instead of their name. Protected health information gathered for this study may be shared with
1012 the third party collaborators. De-identified subject information may also be provided to

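### The DKA list in Section 9.2.2 has no acidosis item, so symptomatic hyperglycemic ketosis treated at a facility is counted as DKA in the primary incidence even when acidosis was ruled out

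*Combined protocol and SAP*

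**What the plan says.** Section 2.6 makes the primary outcome a safety assessment over all six treatment weeks in terms of "incidence of DKA or severe hypoglycemia". Section 11.4 tabulates DKA by treatment group for all randomized participants.

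Section 9.2.2 says that DKA follows the DCCT definition and that this is described further down. The description opens "Hyperglycemic events are classified as DKA if the following are present" and has four bullets:

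1. "symptoms such as polyuria, polydipsia, nausea, or vomiting"
2. "serum ketones ≥ 1.5 mmol/l or large/moderate urine ketones"
3. "treatment provided in a health care facility"
4. a sentence beginning "all reportable Adverse Events—whether volunteered by the participant, discovered by", which tells staff how to report adverse events.

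The same section has a separate reportable category for hyperglycemia or ketosis where "evaluation or treatment was obtained at a health care provider facility for an acute event". Section 9.2 likewise lists DKA and, where DKA is absent, a hyperglycemic or ketosis event as alternatives.

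The DKA label is also used in Section 9.9.1 (two episodes, for a participant) and in Section 9.9.2: "The study must also stop if there are three severe hypoglycemia events or three DKA events".

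**The concern.** The event is called ketoacidosis, but nothing in the list that defines it concerns acidosis. The plan means to distinguish DKA from a ketosis or hyperglycemia visit to a facility, yet for one kind of visit the criteria cannot do so. Since DKA is one of the two events in the primary outcome, a reader of the final report could not tell whether a reported DKA involved acidosis. In a trial of 30 people, the classification of a single visit is visible in the primary figure.

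**Working it through.** **Is an item lost from the text?** The printed line numbers run without a break from 873 to 879 across the list, and nothing there is marked as removed. No pH, bicarbonate or other acidosis criterion is attached to DKA anywhere else in the supplied text. The DCCT definition is not reproduced beyond this list, so an assessor working from the protocol has only these items.

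**Which events fall under both categories?**

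| Event | Meets the DKA list? | Meets the separate facility category? |
|---|---|---|
| Hyperglycemia, facility evaluation only | No (no treatment) | Yes |
| Hyperglycemia treated at a facility, no symptoms | No | Yes |
| Hyperglycemia treated at a facility, ketones below the listed level | No | Yes |
| Symptomatic hyperglycemia, ketones at or above the listed level, treated at a facility, acidosis present | Yes | Yes |
| The same, acidosis ruled out | Yes | Yes |

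The categories separate in the first three rows. The last two rows are treated identically, and that is the gap. The ketone level does not close it: 1.5 mmol/L is also the level in the criterion for a reportable hyperglycemic event with health care provider contact. The ketone-event row in Section 11.4 does not close it either, because it is defined by a day with ketones above 1.0 mmol/L, without reference to acidosis.

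**The plan's own exposure figures (Section 11.2).** With 30 randomized and 6 weeks of treatment, 30 × 6 = 180 participant-weeks. With 15 in the BAM arm, 15 × 6 = 90. Both reproduce. In person-years, 30 × 42 / 365.25 = 3.45.

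**Effect of one such event.** This assumes that incidence is the proportion of participants with an event, and that the affected participant has no other primary event. Intervals are exact (Clopper-Pearson) 95%.

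| Denominator | No event | One event | Change |
|---|---|---|---|
| 30 overall | 0/30 = 0% (0 to 11.6%) | 1/30 = 3.3% (0.1 to 17.2%) | +3.3 points |
| 15 in an arm | 0/15 = 0% (0 to 21.8%) | 1/15 = 6.7% (0.2 to 31.9%) | +6.7 points |

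As a rate, 1 / 3.45 = 0.29 per person-year overall. The zero starting point is illustrative. Arms of 15 are also an assumption, since Section 11.1 allocates by independent Bernoulli draws, which do not guarantee equal arms.

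**What cannot be computed.** The documents give no rate for DKA or for facility-treated ketosis, so neither the expected number of such events nor a corrected incidence can be derived.

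**The case against.** The best defense is that a broad definition errs on the cautious side. It overcounts harm in a safety pilot, and Section 11.4 summarizes the circumstances of each reportable case, so a reader may learn what happened. This has weight as to the consequences. It does not settle the label: the plan does not say that the list is deliberately broader than the definition it cites, and the case summaries are not required to give pH or bicarbonate.

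Four stronger readings are tempting, and the documents do not support them.

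- *Any vomiting illness with raised ketones, treated at a facility, becomes DKA.* It does not. The rule applies only to hyperglycemic events, so hyperglycemia must be present as well as the listed items.
- *One misclassified visit would change the safety conclusion.* No test, threshold or acceptable DKA incidence is tied to the primary outcome. The safety items among the success criteria in Section 11.4 turn on critical module errors and on serious or device-related events attributed to the modules, not on the DKA label. The relatedness guidance in Section 9.3 also takes intercurrent illness into account.
- *Three such visits would end the trial.* They would trigger the stop in Section 9.9.2, but that section allows resumption after medical and safety review if the events are found unrelated to an unanticipated system malfunction.
- *The acidosis cut-offs can simply be taken from the DCCT.* The documents do not reproduce that definition, so neither its cut-offs nor whether it has any can be confirmed here.

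Requiring acidosis outright would also narrow the events counted in Sections 9.9.1 and 9.9.2. That is a clinical and safety decision for the sponsor.

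**Conclusion.** The point holds for one class of event: symptomatic, hyperglycemic, with ketones at or above the listed level, and treated at a facility. For these, the protocol records DKA whether or not acidosis was present, contrary to the separation that Sections 9.2 and 9.2.2 set out to make. This rests on the text alone and does not depend on what the DCCT definition contains. The effect is 3.3 percentage points overall, or 6.7 points in an arm of 15, per participant so classified, under the assumptions stated with the tables. How often this would happen is unknown. What is at stake is whether a component of the primary outcome can be read as ketoacidosis, not a demonstrated bias of known size.

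**What to change.** 1. In Section 9.2.2, reconcile the list with the DCCT definition it cites, and state whether and how acidosis is required.
2. Move the adverse-event reporting sentence out of the list.
3. For every facility-treated event that meets the current list, take any pH or bicarbonate result from the facility's existing record.
4. In Sections 2.6 and 11.4, report these events in three rows: acidosis documented; acidosis not documented, counted as DKA; and acidosis ruled out, shown as ketosis without acidosis. The middle row keeps the count cautious when records are incomplete.
5. State which definition the DKA counts in Sections 9.9.1 and 9.9.2 use. No cut-off is proposed here, and no change to those rules.

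The cost is a few lines of text, additional table rows and a records request for each such visit. No study test is added. The change should be made before any event is classified.
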